4.2. Study population

In the DBCG registry, all HR+/HER2- locally advanced or mBC patients treated with palbociclib in combination with AI as first-line treatment will be identified. Palbociclib was approved by the European Commission (EC) and European Medicines Agency (EMA) in November 2016. Hence, the study period will be from 1 January 2017 and to 31 December 2021. A follow-up on patients until 31 December 2023 in terms of the estimation of PFS and OS will be made. The study will only include patients treated with palbociclib+AI as first-line treatment.

Inclusion Criteria

Patients must meet the following inclusion criteria to be eligible for inclusion in the study:

1. *Patients with breast cancer (ICD-10: DC50)*
2. *A diagnosis of HR+/HER2- locally advanced or metastatic breast cancer*
3. *Endocrine sensitive, endocrine resistant, or de novo mBC patient*
4. *Initiated treatment with palbociclib as first-line treatment (palbociclib + AI) between 1 January 2017 and 31 December 2021*
5. *Inclusion data: Data of relapse/stage IV disease/progression leading to initiation of palbociclib+AI*

Exclusion Criteria

There are no exclusion criteria for this study.

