4.7.1. Index date and follow-up

Definitions of the incidence data and the index date of the first-line treated palbociclib + AI patients shown together with the definition of the treatment outcomes (PFS and OS), as well as definition of visceral disease can be found in the table below.

Incidence date	The date of the initial breast cancer diagnosis.
Index date	The date of relapse or stage IV disease.
Progression Free Survival (PFS)	The time from the date of relapse or stage IV disease (index date) to progression or death, whichever occurs first. Patients will be censored 31 December 2021. Progression is based on radiological, clinical, and biochemical examination from the treating departments.
Overall Survival (OS)	The time from index date to death at any cause.
Visceral disease	Defined as metastases in the organs, e.g., lung, liver. Visceral disease is based on the variable Location of metastases (RE10-18 + 80-81, 117-119, 219-222) in the DBCG database.

For the PFS and OS outcomes for the full palbociclib first-line population (primary analyses) as well as each subpopulation (secondary analyses), as presented below, Kaplan-Meier survival distribution functions with 95% confidence intervals will be estimated. Hence, if possible median PFS and OS as well as interquartile ranges (IQR) will be estimated. Unadjusted Kaplan Meier curves will be presented to illustrate time-to-event (PFS or OS).

For the descriptive statistics, numbers and percentages will be provided and presented in tables, including cross tabulations (see section 6 for presentation of tables shells).

All data analysis will be executed using the statistical software R-studio.

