4.7.2. Primary analyses

As primary analyses (descriptive) of PFS and OS will be estimated for all Danish mBC patients receiving palbociclib as first-line treatment in combination with AI. PFS will be estimated for all patients until either a physician-assessed disease progression occurred, death or until data cut-off by 31 December 2023. OS will be estimated for all patients with a censoring of data by 31 December 2023 as the last day of data capture in the study.

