4.7.3. Secondary analyses

Similar to the primary analyses, univariate analyses of PFS and OS for subgroups (age and comorbidity) of all mBC patients having palbociclib + AI as first-line treatment will be made and with the same definitions and timelines for their estimation.

These subgroups of HR+/ HER2 negative mBC patients are:

Age-groups

- Patients below 65 years of age
- Patients 65-74 years of age
- Patients 75+ years of age

Statistical test of differences in baseline characteristics as well as the PFS and the OS outcomes between each of these age subgroups compared to all first-line palbociclib patients the Shapiro-Wilk test of normality and the Wilcoxon rank sum will be applied.

Palbociclib

A5481188 NON-INTERVENTIONAL STUDY STATISTICAL ANALYSIS PLAN FOR SECONDARY DATA

COLLECTION STUDY

Version 1.0, 1 March 2024

PFIZER CONFIDENTIAL

CT24-WI-GL03-RF03 3.0 *Non-Interventional Statistical Analysis Plan*
for Secondary Data Collection Study

Page 9 of 15

Comorbidities as measured by Charlson Comorbidity Index (CCI)

- Patients split by comorbidity severity score (CCI; 0, 1, 2, and 3 or higher (3+))
- Patients split by number of comorbidities (0, 1, 2+)
- Patients split in types of comorbidities (Cardiac disease, Vascular disease, Metabolic disease, Psychiatric disease, Blood and lymphatic system)

Statistical test of differences in baseline characteristics as well as the PFS and the OS outcomes between each of these comorbidity groups will be performed, e.g. using the chi-square test).

And finally various disease-specific characteristics of the mBC patients having palbociclib + AI as first-line treatment.

- Patients with or without visceral disease
- Bone only patients
- Endocrine resistant, endocrine sensitive or de novo patients

Similar statistical test of difference as for the two other subgroups will be made for the disease-specific characteristics.

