		Patients 65-74 years of age	PFS	Median and IQR
		Patients aged 75+ years of age	PFS	Median and IQR
Secondary	All included patients (first-line treated with palbociclib+AI)	Comorbidities 1 - patients split into severity of comorbidities as measured by CCI (0, 1, 2, 3 or higher (3+))	PFS	Median and IQR
		Comorbidities 2 - patients split into number of comorbidities (0, 1, 2+)	PFS	Median and IQR
		Comorbidities 3 - patients split into type of comorbidities (Cardiac disease, Vascular disease, Metabolic disease, Psychiatric disease, Blood and lymphatic system)	PFS	Median and IQR
Secondary	All included patients (first-line treated with palbociclib+AI)	Patients with visceral disease	PFS	Median and IQR
		Patients without visceral disease	PFS	Median and IQR
Secondary	All included patients (first-line treated with palbociclib+AI)	Patients bone-only	PFS	Median and IQR
		Patients not bone-only	PFS	Median and IQR
Secondary	All included patients (first-line treated with palbociclib+AI)	Endocrine resistant patients	PFS	Median and IQR
		Endocrine sensitive patients	PFS	Median and IQR
		De novo patients	PFS	Median and IQR

Table note: * Following definition of PFS in section 4.7.1.

Table 4. Overall Survival (OS)*. All mBC patients having palbociclib as first-line treatment in combination with AI

Endpoint	Population	Subgroup	Outcome	Result
Primary	All included patients (first-line treated with palbociclib+AI)	All patients	OS	Median and IQR
Secondary	All included patients (first-line treated with palbociclib+AI)	Patients below 65 years of age	OS	Median and IQR
		Patients 65-74 years of age	OS	Median and IQR
		Patients aged 75+ years of age	OS	Median and IQR
Secondary	All included patients (first-line treated with palbociclib+AI)	Comorbidities 1 - patients split into severity of comorbidities as measured by CCI (0, 1, 2, 3 or higher (3+))	OS	Median and IQR
		Comorbidities 2 - patients split into number of comorbidities (0, 1, 2+)	OS	Median and IQR
		Comorbidities 3 - patients split into type of comorbidities (Cardiac disease, Vascular disease, Metabolic disease, Psychiatric disease, Blood and lymphatic system)	OS	Median and IQR
Secondary	All included patients (first-line treated with palbociclib+AI)	Patients with visceral disease	OS	Median and IQR
		Patients without visceral disease	OS	Median and IQR
Secondary	All included patients (first-line treated with palbociclib+AI)	Patients bone-only	OS	Median and IQR
		Patients not bone-only	OS	Median and IQR

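### SAP 4.7.1 censors PFS on 31 December 2021, the last day of inclusion; SAP 4.2 and 4.7.2 say 31 December 2023 and the protocol says 1 February 2024

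*SAP*

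**What the plan says.** The SAP gives two cut-off dates for PFS, and the protocol gives a third.

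- **SAP 4.7.1**, PFS row of the definition table: "Patients will be censored 31 December 2021". The OS row of that table has no censoring date.
- **SAP 4.7.2**, primary analyses: "PFS will be estimated for all patients until either a physician-assessed disease progression occurred, death or until data cut-off by 31 December 2023". For OS: "OS will be estimated for all patients with a censoring of data by 31 December 2023".
- **SAP 4.2**, study population: "A follow-up on patients until 31 December 2023 in terms of the estimation of PFS and OS will be made". Inclusion criterion 4 in the same section requires treatment start "between 1 January 2017 and 31 December 2021".
- **SAP 4.7.3**: the subgroup analyses "will be made and with the same definitions and timelines for their estimation".
- **SAP Appendix A**, note to Table 3 (PFS results): "Following definition of PFS in section 4.7.1".
- **Protocol 8.1** (version 3.0, 17 February 2025) censors PFS and OS on 1 February 2024. Protocol 9.2 and 9.8 agree. The amendment log in protocol section 5 records a move from 31 December 2023 to that date.

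**The concern.** There are two separate discrepancies. The gap between 31 December 2023 and 1 February 2024 is version lag: SAP version 1.0 is dated 1 March 2024, and protocol version 3.0 moved the date almost a year later. The gap between 31 December 2021 and 31 December 2023 is a contradiction inside the SAP. The amendment log never mentions a 2021 censoring date.

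The 2021 date coincides with the end of the inclusion window, so it may be a slip. It nevertheless stands in the formal definition of a primary endpoint, which is the definition the results table cites. If it were followed, PFS would be cut off about two years before OS. A patient who died in 2022 or 2023 without earlier progression would be an OS event but censored for PFS. A patient starting treatment on 31 December 2021 would have no PFS follow-up after treatment start. Because 4.7.3 reuses the definitions and timelines, the conflict also reaches every age and comorbidity subgroup.

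**Working it through.** **1. Follow-up implied by each date** (30.4375 days per month, counted from treatment start).

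| Cut-off | First possible start, 1 Jan 2017 | Last possible start, 31 Dec 2021 |
|---|---|---|
| 31 Dec 2021 | 60.0 months | 0 months |
| 31 Dec 2023 | 83.9 months | 24.0 months |
| 1 Feb 2024 | 85.0 months | 25.0 months |

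The last row reproduces the maximum of 7 years and one month stated in protocol 9.8. The 2021 date takes 24.0 months from each patient compared with SAP 4.2 and 4.7.2, and 25.0 months compared with the protocol.

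**2. Expected PFS events.** From the documents: N = 580 (SAP 4.5) and median PFS of 19.3, 24.8, 27.6 and 31.3 months (protocol section 7). The 31.3-month figure is for endocrine-sensitive first-line patients, whereas this cohort also includes endocrine-resistant patients. Assumed, not in the documents: exponential PFS, uniform accrual over the window, no other censoring, and index date equal to treatment start.

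With λ = ln 2 / median and potential follow-up uniform from a to b months:

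P(event) = 1 − [exp(−λa) − exp(−λb)] / [λ(b − a)]

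Worked case, median 31.3, so λ = 0.02215:

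- 31 Dec 2021 (a = 0, b = 59.96): P = 0.446, and 580 × 0.446 ≈ 259 events.
- 1 Feb 2024 (a = 25.03, b = 84.99): P = 0.682, and 580 × 0.682 ≈ 396 events.
- Loss: 1 − 0.446/0.682 ≈ 34.5%.

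| Median PFS (months) | Events by 31 Dec 2021 | 31 Dec 2023 | 1 Feb 2024 | Loss, 2021 vs 2024 |
|---|---|---|---|---|
| 19.3 | 342 | 479 | 483 | 29.2% |
| 24.8 | 299 | 436 | 440 | 32.2% |
| 27.6 | 280 | 416 | 420 | 33.3% |
| 31.3 | 259 | 391 | 396 | 34.5% |

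**3. Sensitivity to the assumptions.** If accrual falls linearly, the loss is 18.2% to 24.6%; if it rises linearly, 41.8% to 46.6%. If the index date precedes treatment by 3 months, the loss is 25.7% to 31.4% with uniform accrual and 16.2% to 41.9% over all three patterns. The version-lag gap (31 Dec 2023 vs 1 Feb 2024) is about 4 events, or 0.8% to 1.1%, with uniform accrual.

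**4. Effect on the planned estimates.** SAP 4.7.1 says: "Hence, if possible median PFS and OS as well as interquartile ranges (IQR) will be estimated". This was checked by Kaplan-Meier simulation under the step 2 assumptions (1,500 data sets per case, log-log 95% confidence limits).

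- *Overall median, N = 580.* No bias: at a true median of 31.3 months the estimate centres on 31.3 with either date. The typical interval goes from 17.1–21.6 (2024 date) to 16.9–21.9 (2021 date) at a true median of 19.3, and from 27.7–35.1 to 27.1–36.2 at 31.3.
- *Upper quartile (75% event time), N = 580.* With the 2021 date it is not reached in 0%, 6%, 31% and 69% of data sets at the four medians, against at most 0.1% with the 2024 date. At 31.3 months the reason is direct: the exponential 75% time is 2 × 31.3 = 62.6 months, beyond the 60.0 months available. With a 3-month lag the 69% becomes 57%.
- *Illustrative subgroup of 55* (9.5% of 580, the share aged 75 or over in the PALOMA trials, protocol section 7). The upper confidence limit for the median is not reached in 3%, 19%, 30% and 52%, against 0–2% with the 2024 date. The upper quartile is not reached in 11%, 37%, 49% and 64%, against 0.2%, 3%, 8% and 19%.

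**The case against.** The best counter-argument is that this is a clerical slip which the documents largely resolve. Every other statement of the PFS cut-off is later than 2021. Section 4.7.2 is the section that specifies the primary analysis. Protocol 9.8 says that major changes to primary endpoint definitions would be reflected in a protocol amendment, and none sets 2021. The note to Table 4 also points to 4.7.1, where OS has no date, so an analyst must read 4.7.2 for OS and would see the PFS date in the sentence before it. The study is descriptive with no hypothesis tests, and the overall median is hardly affected.

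The size of the harm can also be challenged. The SAP promises medians and IQRs only if possible. With exponential survival, uniform accrual and the quoted OS median of 56.9 months, the OS upper quartile would be unreached in about 97–98% of data sets even at 1 February 2024. The subgroup of 55 borrows a trial share, although the protocol says trials under-represent the elderly. With 116 patients (20%, an assumption), the upper confidence limit for the median is unreached in only about 0%, 2%, 6% and 21% at the four medians.

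Much of this stands. A 2021 analysis is the least supported reading, and the subgroup figures are illustrations. But the SAP has no rule that 4.7.2 overrides 4.7.1, and Table 3 cites 4.7.1. In a descriptive study the estimates are the only product, so the cut-off of a primary endpoint has to be unique.

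**Conclusion.** The concern holds. The dates alone establish it: the PFS definition cited by Table 3 censors on the last inclusion day, against 31 December 2023 elsewhere in the SAP and 1 February 2024 in the current protocol. It must be corrected because it concerns the definition of a primary endpoint, even if it is only a typing error.

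If the 2021 date were applied, the cost would be precision and not bias. About 29% to 35% of the events expected by 1 February 2024 would be lost with uniform accrual, and 16% to 47% over all accrual patterns and lags tried. The effect on the overall median is small. It is larger for the upper quartile when PFS is long, and for small subgroups. These sizes rest on exponential PFS, the assumed accrual, no other censoring, and medians from other studies. Whether the 2021 date was ever used cannot be told from the documents.

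**What to change.** Update the SAP so that PFS and OS share one stated data cut-off, the protocol's 1 February 2024:

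- 4.7.1: replace 31 December 2021 in the PFS row, and add the date to the OS row.
- 4.2: replace 31 December 2023 (one place).
- 4.7.2: replace 31 December 2023 (two places).

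The protocol milestones placed the analyses in April to July 2024, so results may already exist. The sponsor should confirm which cut-off was used for Table 3 and document it.

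The cost is a SAP version update with four dates replaced and one added. No new data are needed for this correction. Table 3 needs to be rerun on account of this error only if it was produced with the 2021 date.

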4.7.2. Primary analyses

As primary analyses (descriptive) of PFS and OS will be estimated for all Danish mBC patients receiving palbociclib as first-line treatment in combination with AI. PFS will be estimated for all patients until either a physician-assessed disease progression occurred, death or until data cut-off by 31 December 2023. OS will be estimated for all patients with a censoring of data by 31 December 2023 as the last day of data capture in the study.

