## 5. AMENDMENTS AND UPDATES

Version Identifier	Date	Amendment Type (substantial or administrative)	Protocol Section(s) Changed	Summary of Amendment(s)	Reason
3.0	17 February 2025	Substantial	3. Responsible Parties 4. Abstracts	Added [name] as a Principal Investigator of the Protocol	Since PPD has left Pfizer, PPD has taken over the responsibility as NI study lead responsible for protocol amendments
	17 February 2025		4. Abstracts	Update of Abstract title	Updated title with correct protocol version number and date
	17 February 2025		4. Abstracts 8.1 Definitions 9.2 Setting 9.8 Data Analysis	Update of OS and PFS censoring date	Due to additional follow-up data available, the censoring date has been changed from 31 st December 2023 to 1 st February 2024

PFIZER CONFIDENTIAL

CT24-WI-GL02-RF02 5.0 Non-Interventional Study Protocol Template For Secondary Data Collection Study 01-Aug-2023

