### 8.1. Definitions

PFS is defined as the date of relapse or stage IV disease (index date) to progression or death, whichever occurs first.

- Patients will be censored for PFS by 1st February 2024
- Progression of disease is based on scans and blood testing results

OS is defined as the date of relapse or stage IV disease (index date) until death of any cause.

- Patients will be censored for OS by 1st February 2024

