## 9. RESEARCH METHODS

### 9.1. Study Design

The study is designed as a secondary data collection NI-Study. Retrospective data will be collected from an existing registry - the DBCG registry. The focus of this study will be on HR+/HER2- locally advanced or metastatic breast cancer treated with palbociclib. The study is a single-arm study focusing on patients treated with palbociclib in Denmark.

The study is purely descriptive and explorative. No formal hypotheses will be tested in the study.

Since the establishment in 1976, the DBCG has maintained a clinical registry for early breast cancer patients in Denmark in which surgeons, pathologists, medical geneticists and oncologists report data regarding diagnosis, treatment and follow-up of breast cancer (39,40). This is a unique clinical registry. This well-established breast cancer registry (1976) managed by DBCG was expanded in 2017 to include retrospective and prospective clinical and pathological data on breast cancer patients with a relapse. This includes both the primary mBC (De Novo) and recurrent mBC.

The DBCG registry focusing on relapses on which the study will be based is one of several DBCG registries. All Danish patients with locally advanced or metastatic breast cancer are included in the DBCG registry. The data and records in the registry are based on systematic review following a standard case report form of all electronic patient records of patients diagnosed with locally advanced or metastatic breast cancer.

PFIZER CONFIDENTIAL

The data collection and the ongoing populating of the DBCG registry are performed by healthcare professionals in the DBCG secretariat and are conducted independently of this study. Compared to other exhaustive national Danish patient registries, the DBCG registry contains detailed clinical and pathological data about the treatment patterns of patients with HR+/HER2- locally advanced or metastatic breast cancer. Thus, the registry is an important and well-suited source to address the research questions of the present study and has previously been used to analyze treatment outcomes for all first- and second-line palbociclib patients in Denmark (29).

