4.3. Variables

The main variables included in the study are the following:

Variable	Role	Data source(s)	DBCG variable(s)
Diagnosis (ICD-10 code: DC50)	Exposure/ Inclusion	DBCG registry	Not applicable
Treatment with palbociclib	Exposure/ Inclusion	DBCG registry	RE201, RE201A
Date of birth	Baseline	DBCG registry	Based on M1
Date of breast cancer diagnosis	Baseline	DBCG registry	Not applicable
Occurrence of metastases	Baseline	DBCG registry	RE220-RE227
Visceral status (visceral and non-visceral – visceral defined as metastases in the organs, e.g., lung, liver))	Baseline	DBCG registry	RE220-RE227
Bone only	Baseline	DBCG registry	RE14
Metastatic sites (liver, lung, CNS, lymph nodes)	Baseline	DBCG registry	RE10-18 + 80-81, 117-119, 219-222
Endocrine resistant (recurrent pts with advanced disease within 12 months of completing adjuvant endocrine therapy or during adjuvant endocrine therapy)	Baseline	DBCG registry	Calculated
Endocrine sensitive (recurrent pts with advanced disease after 12 months of completing adjuvant endocrine therapy, recurrent pts who received no adjuvant endocrine therapy)	Baseline	DBCG registry	Calculated
De Novo (primary mBC – newly metastatic)	Baseline	DBCG registry	Calculated
Date of relapse	Baseline	DBCG registry	RE1-RE3
Date for treatment initiation with palbociclib	Baseline	DBCG registry	RE203-RE205
Date for treatment stop with palbociclib	Baseline	DBCG registry	RE206-RE208
Charlson Comorbidity Index (CCI) – point scores of 0, 1, 2 and 3 or higher (3+) (calculated at start of palbociclib treatment)	Baseline	National Patient Registry data used to define CCI in DBCG registry	Not applicable
Number of comorbidities (calculated at start of palbociclib treatment)	Baseline	National Patient Registry data used to define CCI in DBCG registry	Not applicable
Types of comorbidities (Cardiac disease, Vascular disease, Metabolic disease, Psychiatric disease, Blood and lymphatic system) (at start of palbociclib treatment)	Baseline	National Patient Registry data used to define CCI in DBCG registry	Not applicable
Death date	Baseline charac.	DBCG registry	Not applicable
PFS (see section 8.1 for definition)	Outcome	Estimated via DBCG registry	Based on variables listed in this table
OS (see section 8.1 for definition)	Outcome	Estimated via DBCG registry registrations	Based on variables listed in this table

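### PFS is censored at a calendar date, given in three versions and not tied to how far records were reviewed for progression, so PFS may be overstated

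*SAP*

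**What the plan says.** The documents give three rules for when PFS follow-up ends:

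- SAP 4.7.2: "PFS will be estimated for all patients until either a physician-assessed disease progression occurred, death or until data cut-off by 31 December 2023".
- Protocol 8.1, as amended in version 3.0: "Patients will be censored for PFS by 1 st February 2024".
- SAP 4.7.1, in the PFS definition to which the note under SAP Table 3 refers: "Patients will be censored 31 December 2021".

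On how progression becomes known, SAP 4.7.1 says "Progression is based on radiological, clinical, and biochemical examination from the treating departments". Protocol 9.1 says that data collection and "the ongoing populating of the DBCG registry are performed by healthcare professionals in the DBCG secretariat", independently of this study, and that the study itself reviews no medical records.

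PFS is to be "Based on variables listed in this table" (SAP 4.3; Protocol Table 1 says the same). Neither table names a progression date, a last assessment, a last contact or a date of last record review. SAP Table 3 reports PFS as median and IQR.

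**The concern.** Death and progression reach the data by different routes. A death has a date of its own. A progression is known only once someone has reviewed the record that contains it. A calendar rule treats every patient with no recorded progression or death as observed and progression-free up to the cut-off. If a record was last reviewed some months before, that interval adds time at risk in which no progression could have been seen.

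The error can only go upward. It is partly self-limiting, because a later death still ends PFS, though too late. It matters most in the tail of the curve and so for the upper quartile. As specified, the analyst cannot tell a patient who was progression-free at cut-off from one not yet reviewed. PFS is one of the two primary outcomes, and the subgroup analyses in SAP 4.7.3 use the same definition and timelines. OS depends only on death dates, so a delay in progression review does not affect it.

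**Working it through.** **1. The dates.** Protocol 9.8 states a maximum follow-up of 7 years and one month. From 1 January 2017 to 1 February 2024 is 2,587 days, or 85.0 months, so that figure reproduces. Follow-up from start of treatment under each rule:

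| PFS date | Source | Start 1 Jan 2017 | Start 31 Dec 2021 |
|---|---|---|---|
| 1 Feb 2024 | Protocol 8.1 | 85.0 months | 25.0 months |
| 31 Dec 2023 | SAP 4.7.2 | 83.9 months | 24.0 months |
| 31 Dec 2021 | SAP 4.7.1 | 60.0 months | 0 months |

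The SAP (version 1.0, 1 March 2024) predates the protocol amendment, which explains the second date. The third equals the end of the inclusion period and may be a slip.

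**2. Inputs for the size of the error.**

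- From the documents: 580 patients (Protocol 9.6); entry from 1 January 2017 to 31 December 2021; median PFS 31.3 and OS 56.9 months (Protocol 7, from the earlier Danish registry study, endocrine-sensitive first-line AI group).
- Assumed: uniform entry over 60 months; exponential PFS; 10% of PFS events being deaths; exponential survival after progression, with its mean (26.9 months) set to give a median OS of 56.9; cut-off at month 85; a share of records reviewed only to a fixed lag before cut-off. The documents give neither share nor lag, so both are varied.

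For exponential PFS, the upper quartile is 31.3 × log(4)/log(2) = 62.6 months.

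**3. Calendar rule with lagging records.** Kaplan-Meier on 400,000 simulated patients. With no lag it returns 31.4 and 62.6. Unseen progressions are those after last review and before cut-off, also scaled to 580 patients.

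| Share lagging | Lag (months) | Unseen progressions | Median, deaths known to cut-off | Upper quartile | Median, deaths known only to last review | Upper quartile |
|---|---|---|---|---|---|---|
| 25% | 6 | 1.0% (6) | 31.6 | 64.0 | 31.7 | 64.3 |
| 25% | 12 | 2.2% (13) | 31.9 | 65.5 | 32.1 | 66.9 |
| 50% | 6 | 2.1% (12) | 31.8 | 65.6 | 31.9 | 66.5 |
| 50% | 12 | 4.4% (26) | 32.5 | 69.7 | 33.0 | 74.9 |
| 100% | 6 | 4.1% (24) | 32.3 | 69.8 | 32.6 | 72.9 |
| 100% | 12 | 8.7% (50) | 33.9 | not reached | 35.2 | not reached |

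At the mild end, 25% of records lagging 3 months, the median rises by about 0.1 month and the upper quartile to about 63. With deaths known to cut-off, the largest rise in the median is 33.9 - 31.4 = 2.5 months.

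**4. Scale.** The SD of the Kaplan-Meier median at 580 patients is about √(0.25/580) ÷ (0.5 × log(2)/31.3) = 0.0208/0.0111 = 1.9 months. Simulation also gives 1.9. In the columns with deaths known to cut-off, only the last row exceeds it.

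**5. Do the alternatives work?**

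- Censor every patient without an earlier event at last review, not counting later deaths: median 31.4 in every row, upper quartile 62.5-62.6.
- Censor survivors at last review but still count deaths after it: with a 12-month lag, 31.0 and 60.9 (50% lagging) or 30.7 and 58.8 (all lagging). This overcorrects.

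**The case against.** The documents lean towards complete data. Protocol 9.1 describes a systematic review of all electronic records on a standard form and says the data needed already exist in structured form at study start. SAP 4.6 admits only patients with complete registrations. Planned data collection (6 March to 19 April 2024) starts 34 days after the latest cut-off, and those milestones were not revised in version 3.0, so extraction may have been later still. This stands as a reason not to assume a lag. It does not settle the point, because none of these statements gives the date through which records were reviewed, and complete is not defined.

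A reader might take the amendment's reason, "Due to additional follow-up data available", as evidence that records lag. It is not. It shows the cut-off being moved by one month to match the data at hand, and says nothing about any single patient's record.

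If SAP 4.7.1 governs, the problem almost disappears: a record would have to be about 26 months behind the start of data collection to matter. That is correct, but this date conflicts with SAP 4.7.2 and with the later protocol.

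The study is descriptive, and modest lags move the median by less than sampling error. That also stands. The upper quartile is the more exposed figure, though it is thinly supported in any case. With uniform entry, (85.0 - 62.6)/60 = 37% of patients have follow-up that long, and a quarter of them, about 54 of 580, would still be event-free. SAP 4.7.1 promises the IQR only where it can be estimated.

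**Conclusion.** The point holds as a conditional one. PFS censoring rests on three unreconciled calendar dates, none linked to the extent of progression review. If records stop before the cut-off, PFS may be overstated. For assumed lags of 3-12 months in 25-100% of patients, with deaths known to cut-off, the rise in the median is about 0.1-2.5 months and mostly below the sampling SD of about 1.9 months. The upper quartile goes from 62.6 to 63-70 months, or is not reached. If deaths too are known only to last review, the shifts are larger: up to 3.8 months for the median (35.2 - 31.4).

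Two stronger readings are tempting and unsupported. One is that PFS is overstated as a matter of fact: no passage shows an unreviewed record, and with review complete to the cut-off this source of bias is nil. The other is that age or comorbidity groups are biased unequally: nothing suggests that some groups' records are updated less often, and Protocol 9.1 describes one standard form for all.

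The sizes depend on the assumptions in the check. The 31.3-month median comes from an endocrine-sensitive group, not the full study population.

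**What to change.** 1. Reconcile the PFS date across Protocol 8.1, SAP 4.7.1 and SAP 4.7.2.
2. Set the PFS cut-off at the date through which all records are known to have been reviewed for progression, and state that date. Alternatively, if the registry holds a review date per patient, add it to the variable tables and censor PFS there for every patient without an earlier event. State that deaths after that date are not PFS events in that analysis; without this, the rule overcorrects as shown.
3. Report calendar-date censoring as a sensitivity analysis, and keep the calendar cut-off for OS.

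The cost is a wording change, one extra registry date that neither table now lists, and slightly less PFS follow-up. Censoring at a per-patient review date also assumes that review timing is unrelated to prognosis, which should be stated; a common review-through date avoids that assumption. If the registry confirms that all records were reviewed to the agreed cut-off, one sentence saying so closes the point and the results do not change.
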